7.11.2 The Wisconsin Card Sorting Test

The Wisconsin Card Sorting Test (WCST) is used to measure children's cognitive executive function. WCST is a widely used executive function task proposed by Berg (1948) to assess abstract reasoning and cognitive change in the context of changing environmental contingencies and the ability to cope with changing environmental contingencies³⁻⁵.

The study uses computerized WCST software (Kunming Quanlu Technology Co., Ltd) and is administered to children by professional investigators in a quiet classroom to minimize external distractions. WCST consist of four key cards and one hundred and twenty-eight stimulus cards which depicted four shapes, four colors and four numbers in response. The 4 key cards with the upper features are placed in front of the subject in order from left to right. The stimulus cards are then presented to the subject one at a time and the subject is instructed to match the stimulus card with one of the key cards using either the pictorial, color, or number consistency rules. Subjects are only told whether each response is correct or incorrect. The matching rule is changed once the subject has successfully matched the stimulus card to the key card in succession using the matching rule. The WCST underwent extensive set transfer (i.e., matching rule) across the three categories (color, pictorial and numerical).

7.11.3 The N-BACK Test

The N-back test is a classic working memory task used to assess an individual's working memory capacity and attentional control. The N-back test consists of a 1-back and a 2-back, and each level of the test includes three tests: a colour contrast, a shape contrast, and a position contrast, so there are a total of six tests, namely the 1-back colour test, the 1-back shape test, the 1- back position test, 2-back colour test, 2-back colour test, and 2-back colour test. In this test, the subject's task is to compare the position, colour, or shape of the currently displayed stimulus card with that of a stimulus card in a previous or alternate position. If they are consistent, click the "Confirm" button on the right side of the interface; if they are not consistent, do not click any button. Subjects are asked to focus their attention, constantly update and maintain the stimulus information, and make accurate judgments within a short period of time, this task is designed to examine the short-term memory ability of the subjects as well as their ability to update and maintain the information.

8. Statistical Considerations and Analytical Plan

8.1 Sample size calculation

In this randomized, double-blind crossover study, the sample size is determined according to the relative literature on respiratory outcome⁶⁻⁸, cardiovascular outcome⁹⁻¹⁰, and cognitive function outcome¹¹ and confirmed in PASS15.0 software with the statistical significance of 0.05. Combined with the supporting

evidence and the requirement of sample size calculated in PASS15.0, and considering the typical number of students in each class and the possible withdrawal, we ultimately plan to recruit 100 children for this study.

8.2 Analytical models

We use a linear mixed-effects model to estimate the effects of air purification intervention or per interquartile range (IQR) decrease in personal PM_{2.5} exposure on several functional indicators and targeted biomarkers of children's health. To account for the impact of varied outcome levels at baseline, the absolute or relative change in outcome level is calculated as the difference between post-intervention and pre-intervention, comparing the change in health outcomes between the intervention and control groups after the intervention. We further adjusted for the confounders including sex, age, body mass index (BMI, kg/m²), temperature (°C), relative humidity (%), etc. A random intercept for each participant is included in the models to account for the repeated measurements.

In addition, we plan to perform metabolomics analysis of EBC samples using ultra-high performance liquid chromatography-tandem mass spectrometry and proteomic analysis of serum samples with 4D-label free technology. Besides, other omics analyses and targeted biomarkers of interest are planned to further explore the potential biological mechanisms.

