3.2 Primary and Secondary Outcomes

The primary outcomes for respiratory health are lung function indicators, including forced expiratory volume in 1 s (FEV₁), forced vital capacity (FVC), FEV₁/FVC ratio, peak expiratory flow (PEF), forced expiratory flow at 25–75% of FVC (FEF_{25-75%}), maximal expiratory flow at 75% of FVC (MEF_{75%}), maximal expiratory flow at 50% of FVC (MEF_{50%}), and maximal expiratory flow at 25% of FVC (MEF_{25%}); changes of FeNO; Changes of FeCO. The primary outcomes for cardiovascular health are blood pressure indicators, including systolic blood pressure (SBP), diastolic blood pressure (DBP), mean arterial pressure (MAP) and pulse pressure (PP); heart rate variability indicators, including standard deviation of all normal-to-normal intervals (SDNN), the root mean square of successive differences between adjacent normal cycles (rMSSD), the percentage of adjacent NN interval differences greater than 50 ms (pNN50), very low frequency (VLF), low frequency (LF), high frequency (HF), the ratio of LF to HF (LF/HF); and electrocardiograph parameters, including the interval of the beginning of the P wave to the beginning of the QRS complex (PR interval), the interval of the beginning of Q wave to the end of the S wave (QRS duration), the interval from the onset of the QRS complex to the end of the T wave (QT interval), the QT correction for rate (QTc interval), amplitude of the R wave in lead V5 (RV5), S-wave depth in lead V1 (SV1) and the sum of the R-wave amplitude in lead V5 and the S-wave amplitude in lead V1 (RV5+SV1). The primary outcomes for cognitive health are academic performances, including standardized scores and relative ranking of scores.

The secondary outcomes include the metabolites in exhaled breath condensate, serum protein, the indicators measured by the Wisconsin Card Sorting Test, Attention Network Test, and N-BACK Test. Furthermore, other omics and targeted biomarkers of interest (e.g., CRP, 8-OHdG, etc) are also considered.

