7.10 Academic achievement measurements

Academic achievement is collected at the beginning and end of each study period. The evaluation of academic performance consisted of standardized scores (maths, chinese and total) and the relative ranking of the scores within the grade. Standardized grades are converted from raw grades by z-scores according to the number of exams and class in order to eliminate differences due to different exams; rankings are converted from place rankings of raw grades, reflecting the relative value of grades.

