8.3 Analytical tools

All statistical analyses are carried out in R software. Statistical tests are two-sided, and $p < 0.05$ is considered statistically significant.

9. Criteria for Participant and Study Completion and Premature Study Termination

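### Section 8.2 lets every outcome be analysed as absolute or relative change, with no definition and no rule; percent change cannot be interpreted for the z-score primary outcome, and change scores of either kind waste the pre-period measurement

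*Combined protocol and SAP*

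**What the plan says.** Section 8.2 describes one linear mixed model for the intervention effect "on several functional indicators and targeted biomarkers of children's health", with a random intercept per child. The response is set by one sentence for all outcomes: "the absolute or relative change in outcome level is calculated as the difference between post-intervention and pre-intervention". The formula in that sentence, a difference, describes absolute change only. No section says whether relative change means percent of baseline or a log-ratio, which outcomes use which scale, whether skewed outcomes are transformed, or when the choice is made.

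Section 3.2 lists "changes of FeNO; Changes of FeCO" among the respiratory primary outcomes without a scale. It also states: "The primary outcomes for cognitive health are academic performances, including standardized scores and relative ranking of scores". Section 7.10 explains the scores: "Standardized grades are converted from raw grades by z-scores according to the number of exams and class". Section 8.3 adds "Statistical tests are two-sided" and the 5% threshold. Sections 6.1 and 6.2 provide four surveys, so a pre-period and an end-of-period value exist for each child in each period.

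**The concern.** Three things are at stake.

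- **Meaning.** Percent change divides by the baseline. A z-score is centred on zero and often negative, so dividing by it produces a number with no usable meaning. pNN50 is a percentage that can be zero, and percent change is then undefined. For ranks, percent change distorts: from 2 to 4 is +100%, from 80 to 82 is +2.5%.
- **Error rate.** Two permitted scales for each of about 30 primary indicators leave a choice that could be made after the results are known.
- **Precision.** Section 8.2 uses change scores to deal with differing baselines. In this crossover they carry the noise of the pre-period value into the comparison, where covariate adjustment need not.

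**Working it through.** **Inputs.** From the documents: 100 children (section 8.1; the synopsis gives 105), two periods with pre and post surveys, two-sided 5% tests. The plan gives no effect size, variance or power, so there is no plan figure to reproduce. Assumed here: the distributions, log-SDs and correlations below. Class clustering is ignored, so the rates describe scale choice and baseline handling only.

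**1. Percent change of a z-score.** With roughly normal scores and pre-post correlation ρ, relative change is post/pre − 1. The ratio follows a Cauchy distribution with location ρ and scale √(1 − ρ²), which has no finite mean or variance.

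- Share of children with negative baseline, hence reversed sign: 50%.
- Share of baselines within 0.1 of zero: 2Φ(0.1) − 1 = 8%.
- 95% range at ρ = 0.8: (0.8 − 1) ± 0.6 × 12.71, that is −782% to +742%.
- Simulated for ρ from 0.5 to 0.9: median absolute relative change 0.4 to 1.0, 99th percentile 28 to 55 (2,800% to 5,500%). A t-test on it rejects in only about 2% of null trials.

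**2. False positives from a free choice of scale.** Null simulation of 10,000 trials per setting, two sequences of 50 children, two-sided t-test between sequences on the period difference in change.

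| Outcome type (assumed) | One scale fixed | Better of the two |
|---|---|---|
| Lognormal, log-SD 0.4-0.8, correlation 0.5-0.8 | 4.4-5.4% | 6.3-7.7% |
| Near-symmetric, CV 8-15%, correlation 0.5-0.8 | 4.7-5.2% | 5.2-6.0% |
| z-score, correlation 0.5-0.9 | absolute 4.8-5.5%, percent about 2% | 6.6-7.2% |

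If a log-ratio also counts as relative change, the lognormal range becomes 6.8-9.3%. Two independent tests would give 1 − 0.95² = 9.75%.

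**3. Drift of percent change.** With no true change, the mean percent change of a lognormal outcome is exp(within-child log variance) − 1: +1% at log-SD 0.1 and +43% at 0.6. It occurs under true and sham purification alike. In null runs the mean difference between treatments was within 0.002 of zero.

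**4. Change score against baseline adjustment.** Simulated power was 37-66% for log change and 64-92% for the baseline-adjusted log model, with visits equally correlated and type I error near 5%. Algebra gives the same answer. Let σ² be the visit variance and ρ the correlation between any two visits.

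- Change contrast, (post₁ − pre₁) − (post₂ − pre₂): variance 4σ²(1 − ρ).
- End-of-period contrast, post₁ − post₂: variance 2σ²(1 − ρ). The pre difference is uncorrelated with it.
- The ratio is 1/2, so the expected test statistic grows by √2.
- Power 37%: 1.96 − 0.33 = 1.63; × √2 = 2.30; Φ(2.30 − 1.96) = 63%.
- Power 66%: 1.96 + 0.41 = 2.37; × √2 = 3.36; Φ(3.36 − 1.96) = 92%.

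If visits within a period are more alike, let r be the correlation between the period differences in pre and in post. The ratio becomes (1 + r)/2. At r = 0.5 it is 0.75, and the same two cases rise only to Φ(1.63/√0.75 − 1.96) = 47% and Φ(2.37/√0.75 − 1.96) = 78%.

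The full gain needs the within-child slope. If one common slope b is fitted, it is pulled towards the between-child relation, and with equally correlated visits the ratio is (1 + b²)/2: 0.625 at b = 0.5, and 1 (the change score itself) at b = 1.

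**The case against.** The strongest reply is that the phrase can be read as whichever scale suits the outcome, and that the stated formula is absolute change. Section 8.2 never says that percent change is applied to z-scores. A log-ratio may also already be meant by relative change. This stands: the documents show a missing rule and definition, not a wrong analysis carried out.

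The inflation is also conditional and modest. It requires choosing the scale after seeing results, which the plan leaves open but does not state. If lung function (8 indicators), blood pressure (4) and ECG (7) are near-symmetric, 19 of the 30 indicators in section 3.2 see almost none. A reader might infer that every test fails its 5% level; the figures do not support that. About 30 uncorrected primary tests are a larger error source: 1 − 0.95³⁰ = 79% if independent, which is itself an assumption.

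A reader might also infer that upward drift biases the treatment effect. It does not under the null, because both arms drift equally. Nor does log change always beat percent change: with low variance (between and within log-SD 0.3 and 0.1) and an assumed 4% reduction, both had 53% power.

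Finally, baseline adjustment is separable from the choice of scale. That is true, but the same sentence governs both, and the pre-period values are already collected.

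**Conclusion.** The point holds as a gap in specification with a clear gain available. That percent change is unusable for z-scores follows from the documents' own definition of the outcome; it is a failure of interpretation, since the percent-change test alone rejects too rarely rather than too often. The excess error is about 1 to 3 percentage points per skewed outcome and at most about 1 for near-symmetric ones, and only under post-hoc choice. Which outcomes are skewed is not in the documents; treating FeNO, FeCO or the HRV indices as such is an assumption.

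The precision gain rests on assumed variances, no class clustering and use of the within-child slope. It is largest, a halving of variance, when all visits are equally correlated, and shrinks towards nothing as visits within a period become more alike.

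The document is dated September 2024 and the study ran April to December 2021. A reader might infer that the scale was left open until results were known. The date does not show when section 8.2 was written, so that is not supported; equally, nothing shows that the scale was fixed before data were available.

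**What to change.** In section 8.2, replace the absolute-or-relative change response by a mixed model of the end-of-period value with the pre-period value as covariate, entered as the child's mean pre-period value and the deviation from it so that the within-child slope is used. Fix one scale per outcome:

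- original scale for z-scores, ranks, lung function, blood pressure and ECG;
- log scale, reported as a ratio of geometric means, for FeNO, FeCO and HRV indices where right-skewed;
- original scale for pNN50 and any outcome with zeros.

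State that percent change is not used for z-scores or ranks, and label any other scale as a sensitivity analysis. If outcome data have already been seen, disclose for each outcome the scale used and when it was chosen; new wording cannot then restore pre-specification.

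The cost is wording and re-running the models; no new data are needed. Logged outcomes are reported as ratios, and estimates are no longer simple mean changes.

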3.1 Description of Study Design

A cluster-randomized, double-blind, crossover trial of a multi-setting (classroom and bedroom) air purification intervention is conducted in Mengzhou City, Henan Province, China, from April 2021 to December 2021. Children aged 10–12 years old (fourth grade) are recruited as subjects. Participants are divided into an intervention group and a control group according to the principle of cluster randomization. The intervention group is equipped with true-particulate air purifiers and the control group is equipped with sham-purification devices both in bedrooms and school classrooms. The two groups receive alternating treatments of true or sham purification in a random order, with each study period separated by a washout period of over two months. A linear mixed-effects model is used to explore the effects of purification intervention. Ambient PM_{2.5} and indoor PM_{2.5} exposure concentrations are monitored in the study.

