3.3 Stratification, Randomization, and Blinding

Students are allocated by class cluster randomization to the intervention group or the control group. The intervention assignment is handed over to independent trained professionals, who do not participate in

any other processes of the trial. Confidentiality of the intervention is maintained for the researcher and participants to achieve double blindness.

4. Participants and Sites

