6.1 Intervention

The intervention group is equipped with purifiers with true-purification (i.e., with high-efficiency particulate air (HEPA) filter), and the control group with sham-purification purifiers (without HEPA filter), which are installed in the classrooms and households of both groups. In the school environment, an air purification efficiency of 850 m³/h (LEXY, KJ901) and a fresh air ventilation with the purification efficiency of 320 m³/h (AIRTAO, AT320) are placed in the front of the classroom and the air purification equipment is the same as the back of classroom. In the home environment, one air purifier with the purification efficiency of 220 m³/h (Haier, KJ210F-A180A) is installed in each of the children's bedroom. Two different treatments are employed, including true-purification and sham-purification, in random order with a washout period of over 2 months. The air purification intervention is performed by trained professionals on and off at regular intervals each day to ensure that the air purification unit is on during the time the children are in the indoor environment. In the event of offline situations such as those caused by poor internet access, the survey respondents are contacted and communicated with promptly. A health examination is conducted at the beginning and end of each study period, and a questionnaire is used to collect basic information about the respondents. We also measured the environmental factors including

PM_{2.5} concentration, temperature, and relative humidity. 24 time-weighted mean PM_{2.5} concentrations are calculated as personal daily exposures for further analysis.

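### Whole classes are randomised, but the 8.2 treatment model has only a child random intercept and no period or class-by-period term, so its 5% test is not reliable

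*Combined protocol and SAP*

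**What the plan says.** Section 3.1 states "Participants are divided into an intervention group and a control group according to the principle of cluster randomization". Section 3.3 makes the cluster explicit: "Students are allocated by class cluster randomization to the intervention group or the control group". Section 7.2 repeats it.

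On measurement, section 6.1 says "A health examination is conducted at the beginning and end of each study period". Section 8.2 then defines the response within each period: "the absolute or relative change in outcome level is calculated as the difference between post-intervention and pre-intervention". Each child therefore contributes two change scores, one under true and one under sham purification.

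Section 8.2 fits a linear mixed-effects model. On covariates it says "We further adjusted for the confounders including sex, age, body mass index", followed by temperature, relative humidity and an open-ended 'etc.'. On random effects it says "A random intercept for each participant is included in the models to account for the repeated measurements". No class, class-by-period, period or sequence term is named, and no cluster-robust, class-level or small-sample method. Section 8.3 adds "Statistical tests are two-sided" and a 0.05 threshold.

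Section 8.1 plans 100 children, "considering the typical number of students in each class and the possible withdrawal". It gives no number of classes and no intraclass correlation.

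**The concern.** Treatment varies only between class-by-period cells: in a given period, every child in a class has the same treatment. Anything that shifts the change score of a whole class in one period and not the other falls on the treatment contrast. An infection in one class at one survey is an example. A child intercept cannot represent such a shift, because it is shared across children and not across a child's two periods. The model divides this variation by the number of children when it should be divided by the number of classes. Intervals are then too narrow and the 5% test rejects too often.

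A missing period term is a different problem. The study runs from April to December 2021, so a shift in change common to all children between the two periods is plausible. Without a period term the shift goes into the residual, into the treatment estimate, or into both.

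This model is the only stated basis for inference on the treatment effect, so it bears on nearly all the primary outcomes.

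**Working it through.** **Inputs from the documents.** Class is the unit of randomisation (3.3, 7.2). There are two periods, each with a pre and a post survey (6.1, 6.2). The response is change, with a child intercept only (8.2). The test is two-sided at 5% (8.3). There are 100 children (8.1; the synopsis gives 105, and 100 is used here). The 100 cannot be reproduced, because 8.1 gives no effect size, SD, power or correlation.

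**Assumed, because the documents are silent.** Number of classes K = 2, 4 or 10, of equal size m. Intraclass correlation (ICC) = 0, 0.01 or 0.05.

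**Definition.** D is a child's change in period 2 minus change in period 1, scaled to SD 1. ICC is the correlation of D between classmates.

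**Step 1: what cancels.** A constant class effect cancels in absolute change. So does a class condition that is equal at both surveys of a period. A four-survey simulation with period adjusted for gives these error rates for 2x50 / 4x25 / 10x10:
- stable class effect only: 4.9 / 4.3 / 5.4%
- class-by-period effect equal at both surveys of a period: 4.6 / 5.1 / 5.0%
- class effect specific to a survey, giving ICC 0.01: 10.8 / 7.5 / 6.2%
- the same, giving ICC 0.05: 29.9 / 19.7 / 10.1%

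Only the last two kinds do harm.

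**Step 2: true error with period adjusted for, or with no period shift.** Design effect DE = 1 + (m-1)ICC. True error = 2(1 - Phi(1.96/sqrt(DE))). For 2 classes at ICC 0.05, DE = 1 + 49 x 0.05 = 3.45, 1.96/sqrt(3.45) = 1.055, and the error is 29.1%.

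| Classes | DE at ICC 0.01 / 0.05 | Error at ICC 0 / 0.01 / 0.05 | Simulated at 0.01 / 0.05 |
|---|---|---|---|
| 2 of 50 | 1.49 / 3.45 | 5.0 / 10.8 / 29.1% | 11.3 / 30.7% |
| 4 of 25 | 1.24 / 2.20 | 5.0 / 7.8 / 18.6% | 7.7 / 18.9% |
| 10 of 10 | 1.09 / 1.45 | 5.0 / 6.0 / 10.4% | 6.0 / 10.7% |

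The plan's nominal 5% is recovered only at ICC 0.

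**Step 3: period omitted.** Each child's true-minus-sham contrast is +D in one sequence and -D in the other. A common shift s in D therefore averages to a bias of s x (nA - nB)/N in absolute size.
- Equal sequences: the bias is 0. The shift inflates the residual and the test becomes stricter.
- 60/40 split: (60 - 40)/100 = 0.2. The bias is 0.2 x 0.5 = 0.10 SD for a shift of 0.5 SD, and 0.2 x 1.0 = 0.20 SD for a shift of 1.0 SD, in SDs of D. Simulation reproduces both.

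**Step 4: information at class level.** There are 2K class-by-period means. Fitting K class effects, one period effect and one treatment effect leaves 2K - (K + 2) = K - 2 degrees of freedom: 0, 2 and 8 for K = 2, 4 and 10. With 2 classes, a class-by-period difference cannot be told apart from a treatment effect at any ICC.

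**The case against.** The strongest reply is that the crossover and the change score already deal with class effects. For stable class differences in absolute change this is right, and it stands. It does not reach class-level variation in change that differs between periods.

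A second reply is that temperature, humidity and 'etc.' cover the gap. They may absorb part of a common period shift. They are not a period term, and an open-ended list does not specify one. Nor do they model the remaining correlation between classmates.

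A third reply is that the error rates rest on assumed values. That stands too. The K - 2 degrees of freedom, however, need no ICC.

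Three stronger readings are tempting, and the documents do not support them.
- A reader might infer that the trial's error rate is 29%. That needs two classes and an ICC of 0.05, and neither is stated. The class-size remark in 8.1 does not fix the number of classes.
- A reader might try to net the two faults, reasoning that with balanced sequences they offset when the squared shift equals (m-1)ICC. That is not general. A random-intercept model cannot have a negative child variance, so the widening depends on the correlation between a child's two change scores, which is not given. For 2 classes at ICC 0.05 the supposed balance point is sqrt(49 x 0.05) = 1.57 SD. Simulated error there is about 11% at correlation 0 and 8 to 9% at correlation 0.3. No single break-even shift or fixed error rate should be quoted for the model without period.
- A reader might apply the inflation figures to every primary outcome. Section 7.10 standardises academic scores by exam and class, which can remove class-level differences altogether. The figures do not apply to those z-scores.

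**Conclusion.** The point holds for the treatment contrast in 8.2. The analysis does not reflect the randomised unit, so the two-sided 5% test cannot be relied on. With period adjusted for or no shift, any positive ICC makes it too liberal: about 6 to 11% at ICC 0.01 and 10 to 29% at ICC 0.05 across 10 down to 2 classes. At ICC 0 it is correct. With period omitted, the test is stricter under equal sequences, by an amount the documents do not let one fix. Under unequal sequences the estimate is biased, by 0.10 to 0.20 SD in the 60/40 example. The net direction for this trial is unknown.

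That the terms are missing is read directly from the text. The sizes rest on assumed class numbers, equal class sizes, ICC and period shift. The cancellation of stable class effects is exact for absolute change only. The figures are not claimed for the PM2.5 model or the class-standardised academic scores. The point must be fixed.

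**What to change.** In 8.2, for the treatment contrast on change scores:

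1. Keep the child random intercept. Add fixed effects for period and class and a class-by-period random intercept, with Kenward-Roger or Satterthwaite degrees of freedom. Alternatively, compare class-mean period differences between the two sequences on K - 2 degrees of freedom.
2. State the number of classes and of children in each sequence.
3. Except the class-standardised academic z-scores from the class-level test, because standardising within class can remove a treatment effect along with the class differences.
4. If there are only 2 classes, no class-level test exists. Keep the child-level model with a period term and state that its p-values assume no class-by-period variation in change. Show intervals widened by sqrt(1 + (m-1)ICC) for ICC 0 to 0.05 (with 50 per class, sqrt(1.49) = 1.22 times at 0.01 and sqrt(3.45) = 1.86 times at 0.05). Limit the conclusions to match.
5. Label the revised analysis with its date. The document is dated 2024-09-12, after the planned end of the study in December 2021.

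**Cost.** No new data are needed, since class was the unit of allocation. The price is wider intervals and lower power. Take an effect with nominal 80% child-level power, so that the non-centrality is 2.80/sqrt(DE). A class-level t test then has about 30% power at ICC 0.01 and 20% at ICC 0.05 with 4 classes, and 65% and 53% with 10.
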